Grade 3 or 4		
For Grade 3: Hold study drug/study regimen until resolution to Grade ≤ 1 or baseline. If temporarily holding the study drug/study regimen does not provide improvement of the Grade 3 skin rash to Grade ≤ 1 or baseline within 30 days, then permanently discontinue study drug/study regimen.
 
For Grade 4: Permanently discontinue study drug/study regimen.
	
For Grade 3 or 4:
 
 – Consult dermatology. – Promptly initiate empiric IV methylprednisolone 1 to 4 mg/kg/day or equivalent. – Consider hospitalization. – Monitor extent of rash [Rule of Nines]. – Consider skin biopsy (preferably more than 1) as clinically feasible. – Once the patient is improving, gradually taper steroids over ≥ 28 days and consider prophylactic antibiotics, antifungals, and anti-PCP treatment (refer to current NCCN guidelines for treatment of cancer-related infections [Category 2B recommendation]).^a – Discuss with study physician.
Endocrinopathy (eg, hyperthyroidism, hypothyroidism, hypopituitarism, and adrenal insufficiency)	Any Grade (depending on the type of endocrinopathy, refer to NCI CTCAE v4.03 for	General Guidance	
For Any Grade:
 
 – Consult endocrinologist. – Monitor patients for signs and symptoms of endocrinopathies. Non-specific symptoms include headache, fatigue, behavior

Specific Immune-mediated Reactions

Adverse Events	Severity Grade of the Event (NCI CTCAE version 4.03)	Dose Modifications	Toxicity Management
	defining the CTC grade/severity)		
changes, changed mental status, vertigo, abdominal pain, unusual bowel habits, hypotension, and weakness.
 
 – Patients should be thoroughly evaluated to rule out any alternative etiology (eg, disease progression including brain metastases, or infections). – Monitor and evaluate thyroid function tests: TSH, free T3 and free T4 and other relevant endocrine labs depending on suspected endocrinopathy. – If a patient experiences an AE that is thought to be possibly of autoimmune nature (eg, thyroiditis, pancreatitis, hypophysitis, or diabetes insipidus), the investigator should send a blood sample for appropriate autoimmune antibody testing.
Grade 1	No dose modifications.		
For Grade 1 (including those with asymptomatic TSH elevation):
 
 – Monitor patient with appropriate endocrine function tests. – If TSH < 0.5 × LLN, or TSH > 2 × ULN or consistently out of range in 2 subsequent measurements, include free T4 at subsequent cycles as clinically indicated and consider endocrinology consult.
Grade 2	
For Grade 2 endocrinopathy other than hypothyroidism, hold study drug/study regimen dose until patient is clinically stable.
 
 • If toxicity worsens, then treat as Grade 3 or Grade 4. 
Study drug/study regimen can be resumed once event stabilizes and after completion of steroid taper.
		
For Grade 2 (including those with symptomatic endocrinopathy):
 
 – Isolated hypothyroidism may be treated with replacement therapy without treatment interruption and without corticosteroids. – Initiate hormone replacement as needed for management. – Evaluate endocrine function, and as clinically indicated, consider pituitary scan.

Specific Immune-mediated Reactions

Adverse Events	Severity Grade of the Event (NCI CTCAE version 4.03)	Dose Modifications	Toxicity Management
		
Patients with endocrinopathies who may require prolonged or continued steroid replacement can be retreated with study drug/study regimen on the following conditions:
 
 1. The event stabilizes and is controlled. 2. The patient is clinically stable as per investigator or treating physician's clinical judgement. 3. Doses of prednisone are ≤ 10 mg/day or equivalent. 	
 – For patients with abnormal endocrine work up, except for those with isolated hypothyroidism, consider short-term corticosteroids (eg, 1 to 2 mg/kg/day methylprednisolone or IV equivalent) and prompt initiation of treatment with relevant hormone replacement (eg, levothyroxine, hydrocortisone, or sex hormones). – – Once the patient is improving, gradually taper steroids over ≥ 28 days and consider prophylactic antibiotics, antifungals, and anti-PCP treatment (refer to current NCCN guidelines for treatment of cancer-related infections [Category 2B recommendation]).^a – For patients with normal endocrine workup (laboratory assessment or MRI scans), repeat laboratory assessments/MRI as clinically indicated.
Grade 3 or 4	For Grade 3 or 4 endocrinopathy other than hypothyroidism, hold study drug/study regimen dose until endocrinopathy symptom(s) are controlled. Study drug/study regimen can be resumed once event stabilizes and after completion of steroid taper.	For Grade 3 or 4:	
 – Consult endocrinologist. – Isolated hypothyroidism may be treated with replacement therapy without treatment interruption and without corticosteroids. – Promptly initiate empiric IV methylprednisolone 1 to 2 mg/kg/day or equivalent – Administer hormone replacement therapy as necessary. – For adrenal crisis, severe dehydration, hypotension, or shock, immediately initiate IV corticosteroids with mineralocorticoid activity. – Once the patient is improving, gradually taper

Specific Immune-mediated Reactions

Adverse Events	Severity Grade of the Event (NCI CTCAE version 4.03)	Dose Modifications	Toxicity Management
			
immunosuppressive steroids over ≥28 days and consider prophylactic antibiotics, antifungals, and anti-PCP treatment (refer to current NCCN guidelines for treatment of cancer-related infections [Category 2B recommendation]).^a
 
 – Discuss with study physician.
Neurotoxicity (to include but not be limited to limbic encephalitis and autonomic neuropathy, excluding Myasthenia Gravis and Guillain-Barre)	Any Grade (depending on the type of neurotoxicity, refer to NCI CTCAE v4.03 for defining the CTC grade/severity)	General Guidance	
For Any Grade:
 
 – Patients should be evaluated to rule out any alternative etiology (eg, disease progression, infections, metabolic syndromes, or medications). – Monitor patient for general symptoms (headache, nausea, vertigo, behavior change, or weakness). – Consider appropriate diagnostic testing (eg, electromyogram and nerve conduction investigations). – Perform symptomatic treatment with neurological consult as appropriate.
Grade 1	No dose modifications.		
For Grade 1:
 
 – See “Any Grade” recommendations above.
Grade 2	
For acute motor neuropathies or neurotoxicity, hold study drug/study regimen dose until resolution to Grade ≤1.
 
For sensory neuropathy/neuropathic pain, consider holding study drug/study regimen dose until resolution to Grade ≤1.
 
If toxicity worsens, then treat as Grade 3 or 4.
 
Study drug/study regimen can be resumed once event improves to Grade ≤1 and
		
For Grade 2:
 
 – Discuss with the study physician. – Obtain neurology consult. – Sensory neuropathy/neuropathic pain may be managed by appropriate medications (eg, gabapentin or duloxetine). – Promptly start systemic steroids prednisone 1 to 2 mg/kg/day PO or IV equivalent. – If no improvement within 3 to 5 days despite 1 to 2 mg/kg/day prednisone PO or IV equivalent, consider additional workup and promptly treat with additional

Specific Immune-mediated Reactions

Adverse Events	Severity Grade of the Event (NCI CTCAE version 4.03)	Dose Modifications	Toxicity Management
		after completion of steroid taper.	immunosuppressive therapy (eg, IV IG).
	Grade 3 or 4 
For Grade 3: Hold study drug/study regimen dose until resolution to Grade ≤1. Permanently discontinue study drug/study regimen if Grade 3 irAE does not resolve to Grade ≤1 within 30 days.
 
For Grade 4: Permanently discontinue study drug/study regimen.
	For Grade 3 or 4: 
 Discuss with study physician. Obtain neurology consult. Consider hospitalization. Promptly initiate empiric IV methylprednisolone 1 to 2 mg/kg/day or equivalent. If no improvement within 3 to 5 days despite IV corticosteroids, consider additional workup and promptly treat with additional immunosuppressants (eg, IV IG). Once stable, gradually taper steroids over ≥28 days. 	
Peripheral neuromotor syndromes (such as Guillain-Barre and myasthenia gravis)	Any Grade	General Guidance	For Any Grade: 
 The prompt diagnosis of immune-mediated peripheral neuromotor syndromes is important, since certain patients may unpredictably experience acute decompensations that can result in substantial morbidity or in the worst case, death. Special care should be taken for certain sentinel symptoms that may predict a more severe outcome, such as prominent dysphagia, rapidly progressive weakness, and signs of respiratory insufficiency or autonomic instability. Patients should be evaluated to rule out any alternative etiology (eg, disease progression, infections, metabolic syndromes or medications). It should be noted that the diagnosis of immune-mediated peripheral neuromotor syndromes can be particularly challenging in patients with underlying cancer, due to the multiple potential confounding effects of cancer (and its treatments) throughout the neuraxis. Given the

Specific Immune-mediated Reactions

Adverse Events	Severity Grade of the Event (NCI CTCAE version 4.03)	Dose Modifications	Toxicity Management
			
importance of prompt and accurate diagnosis, it is essential to have a low threshold to obtain a neurological consult.
 
 – Neurophysiologic diagnostic testing (eg, electromyogram and nerve conduction investigations, and “repetitive stimulation” if myasthenia is suspected) are routinely indicated upon suspicion of such conditions and may be best facilitated by means of a neurology consultation. – It is important to consider that the use of steroids as the primary treatment of Guillain-Barre is not typically considered effective. Patients requiring treatment should be started with IV IG and followed by plasmapheresis if not responsive to IV IG.
	Grade 1	No dose modifications.	
For Grade 1:
 
 – Discuss with the study physician. – Care should be taken to monitor patients for sentinel symptoms of a potential decompensation as described above. – Obtain a neurology consult unless the symptoms are very minor and stable.
	Grade 2	
Hold study drug/study regimen dose until resolution to Grade ≤ 1.
 
Permanently discontinue study drug/study regimen if it does not resolve to Grade ≤ 1 within 30 days or if there are signs of respiratory insufficiency or autonomic instability.
	
For Grade 2:
 
 – Discuss with the study physician. – Care should be taken to monitor patients for sentinel symptoms of a potential decompensation as described above. – Obtain a neurology consult – Sensory neuropathy/neuropathic pain may be managed by appropriate medications (eg, gabapentin or duloxetine). 
MYASTHENIA GRAVIS:
 
 ○ Steroids may be successfully used to

Specific Immune-mediated Reactions

Adverse Events	Severity Grade of the Event (NCI CTCAE version 4.03)	Dose Modifications	Toxicity Management
			
treat myasthenia gravis. It is important to consider that steroid therapy (especially with high doses) may result in transient worsening of myasthenia and should typically be administered in a monitored setting under supervision of a consulting neurologist.
 
 ○ Patients unable to tolerate steroids may be candidates for treatment with plasmapheresis or IV IG. Such decisions are best made in consultation with a neurologist, taking into account the unique needs of each patient. ○ If myasthenia gravis-like neurotoxicity is present, consider starting AChE inhibitor therapy in addition to steroids. Such therapy, if successful, can also serve to reinforce the diagnosis. 
GUILLAIN-BARRE:
 
 ○ It is important to consider here that the use of steroids as the primary treatment of Guillain-Barre is not typically considered effective. ○ Patients requiring treatment should be started with IV IG and followed by plasmapheresis if not responsive to IV IG.

Specific Immune-mediated Reactions

Adverse Events	Severity Grade of the Event (NCI CTCAE version 4.03)	Dose Modifications	Toxicity Management
	Grade 3 or 4	
For Grade 3: Hold study drug/study regimen dose until resolution to Grade ≤ 1. Permanently discontinue study drug/study regimen if Grade 3 irAE does not resolve to Grade ≤ 1 within 30 days or if there are signs of respiratory insufficiency or autonomic instability.
 
For Grade 4: Permanently discontinue study drug/study regimen.
	
For Grade 3 or 4 (severe or life-threatening events):
 
 – Discuss with study physician. – Recommend hospitalization. – Monitor symptoms and obtain neurological consult. 
MYASTHENIA GRAVIS:
 
 ○ Steroids may be successfully used to treat myasthenia gravis. They should typically be administered in a monitored setting under supervision of a consulting neurologist. ○ Patients unable to tolerate steroids may be candidates for treatment with plasmapheresis or IV IG. ○ If myasthenia gravis-like neurotoxicity present, consider starting AChE inhibitor therapy in addition to steroids. Such therapy, if successful, can also serve to reinforce the diagnosis. 
GUILLAIN-BARRE:
 
 ○ It is important to consider here that the use of steroids as the primary treatment of Guillain-Barre is not typically considered effective. ○ Patients requiring treatment should be started with IV IG and followed by plasmapheresis if not responsive to IV IG.

- (ii) ^a ASCO Educational Book 2015 "Managing Immune Checkpoint Blocking Antibody Side Effects" by Michael Postow MD.
- (iii) ^b FDA Liver Guidance Document 2009 Guidance for Industry: Drug Induced Liver Injury – Premarketing Clinical Evaluation.
- (iv) AChE Acetylcholine esterase; ADL Activities of daily living; AE Adverse event; ALP Alkaline phosphatase test; ALT Alanine aminotransferase; AST Aspartate aminotransferase; BUN Blood urea nitrogen; CT Computed tomography; CTCAE Common Terminology Criteria for Adverse Events; ILD Interstitial lung disease; irAE Immune-related adverse event; IG Immunoglobulin; IV Intravenous; GI Gastrointestinal; LFT Liver function tests; LLN Lower limit of normal; MRI Magnetic resonance imaging; NCI National Cancer Institute; NCCN National Comprehensive Cancer Network; PCP ; PO By mouth; T3 Triiodothyronine; T4 Thyroxine; TB Total bilirubin; TNF Tumor necrosis factor; TSH Thyroid-stimulating hormone; ULN Upper limit of normal.

Infusion-related Reactions

Severity Grade of the Event (NCI CTCAE version 4.03)	Dose Modifications	Toxicity Management
Any Grade	General Guidance	
For Any Grade:
 
 – Manage per institutional standard at the discretion of investigator. – Monitor patients for signs and symptoms of infusion-related reactions (eg, fever and/or shaking chills, flushing and/or itching, alterations in heart rate and blood pressure, dyspnea or chest discomfort, or skin rashes) and anaphylaxis (eg, generalized urticaria, angioedema, wheezing, hypotension, or tachycardia).
Grade 1 or 2	
For Grade 1: The infusion rate of study drug/study regimen may be decreased by 50% or temporarily interrupted until resolution of the event.
 
For Grade 2: The infusion rate of study drug/study regimen may be decreased 50% or temporarily interrupted until resolution of the event.
 
Subsequent infusions may be given at 50% of the initial infusion rate.
	
For Grade 1 or 2:
 
 – Acetaminophen and/or antihistamines may be administered per institutional standard at the discretion of the investigator. – Consider premedication per institutional standard prior to subsequent doses. – Steroids should not be used for routine premedication of Grade ≤ 2 infusion reactions.
Grade 3 or 4	
For Grade 3 or 4: Permanently discontinue study drug/study regimen.
	
For Grade 3 or 4:
 
 – Manage severe infusion-related reactions per institutional standards (eg, IM epinephrine, followed by IV diphenhydramine and ranitidine, and IV glucocorticoid).

(v) CTCAE Common Terminology Criteria for Adverse Events; IM Intramuscular; IV Intravenous; NCI National Cancer Institute.

Non-immune-mediated Reactions

Severity Grade of the Event (NCI CTCAE version 4.03)	Dose Modifications	Toxicity Management
Any Grade	Note: Dose modifications are not required for AEs not deemed to be related to study treatment (ie, events due to underlying disease) or for laboratory abnormalities not deemed to be clinically significant.	Treat accordingly, as per institutional standard.
Grade 1	No dose modifications.	Treat accordingly, as per institutional standard.
Grade 2	Hold study drug/study regimen until resolution to ≤Grade 1 or baseline.	Treat accordingly, as per institutional standard.
Grade 3	Hold study drug/study regimen until resolution to ≤Grade 1 or baseline. For AEs that downgrade to ≤Grade 2 within 7 days or resolve to ≤Grade 1 or baseline within 14 days, resume study drug/study regimen administration. Otherwise, discontinue study drug/study regimen.	Treat accordingly, as per institutional standard.
Grade 4	Discontinue study drug/study regimen (Note: For Grade 4 labs, decision to discontinue should be based on accompanying clinical signs/symptoms, the Investigator's clinical judgment, and consultation with the Sponsor.).	Treat accordingly, as per institutional standard.

(vi) Note: As applicable, for early phase studies, the following sentence may be added: "Any event greater than or equal to Grade 2, please discuss with Study Physician."
 (vii) AE Adverse event; CTCAE Common Terminology Criteria for Adverse Events; NCI National Cancer Institute.

Appendix 2**Schedule of study procedures: follow-up for subjects who have completed durvalumab and tremelimumab treatment and achieved disease control (until confirmed progression of disease) and subjects who have discontinued durvalumab or tremelimumab due to toxicity in the absence of confirmed progression of disease**

Evaluation	Time Since Last Dose of MEDI4736							12 Months and Every 6 Months (± 2 weeks)	
	Day (± 3)	Months (± 1 week)							
	30	2	3	4	6	8	10		
Physical examination	X								
Vital signs (temperature, respiratory rate, blood pressure, pulse)	X								
Weight	X								
AE/SAE assessment	X	X	X						
ECOG performance status	X								
Subsequent anti-cancer therapy	X	X	X	X	X	X	X		
Survival status: phone contact with subjects who refuse to return for evaluations and agree to be contacted		X	X	X	X	X	X	X (every 2 months)	
Hematology	X							X	
Serum chemistry	X								
Tumour assessment (CT or MRI)		For subjects who achieve disease control following 12 months of treatment , tumour assessments should be performed every 8-12 weeks relative to the date of first infusion thereafter until confirmed PD by RECIST 1.1 by investigational site review. For subjects who discontinue MEDI4736 due to toxicity (or symptomatic deterioration) , tumour assessments should be performed relative to the date of first infusion as follows: every 8-12 weeks until confirmed PD by RECIST 1.1 by investigational site review. Upon confirmed PD, scans should be conducted according to local standard clinical practice							

Appendix 3**Schedule of study procedures: follow-up for subjects who have discontinue durvalumab and tremelimumab treatment due to confirmed progression of disease at the investigator discretion**

Evaluation	Time Since Last Dose of MEDI4736							12 Months and Every 6 Months (±2 weeks)	
	Day (±3)	Months (±1 week)							
	30	2	3	4	6	8	10		
Physical examination	X								
Vital signs (temperature, respiratory rate, blood pressure, pulse)	X								
Weight	X								
AE/SAE assessment	X	X	X						
ECOG performance status	X	X	X						
Survival status: phone contact with subjects who refuse to return for evaluations and agree to be contacted		X	X	X	X	X	X	X (every 2 months)	
Hematology	X								
Serum chemistry	X								
Tumour assessment (CT or MRI)		For subjects who continue on MEDI4736 post-confirmed progression at the investigator's discretion (following consultation with the sponsor), tumour assessments should be performed relative to the date of first infusion until MEDI4736 is stopped. For subjects who discontinue MEDI4736 following confirmed progression , scans should be conducted according to local clinical practice.

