Subjects may withdraw consent at any time for any reason or be dropped from the trial at the discretion of the investigator should any untoward effect occur. In addition, a subject may be withdrawn by the investigator or the Sponsor if enrollment into the trial is inappropriate, the trial plan is violated, or for administrative and/or other safety reasons.

Subjects who are permanently discontinued from receiving investigational product will be allowed for safety per Appendix 2 or 3, including the collection of any protocol-specified blood specimens, unless consent is withdrawn or the subject is lost to follow-up or enrolled in another clinical study. All subjects will be followed for survival. Subjects who decline to return to the site for evaluations will be offered follow-up by phone every 3 months as an alternative.

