8.1.3 End of Treatment

End of treatment is defined as the last planned dosing visit within the 12-month dosing period. For subjects who discontinue durvalumab or tremelimumab prior to completing all 13 cycles, end of treatment is considered the last visit where the decision is made to discontinue treatment. All required procedures may be completed within \pm 7 days of the end of treatment visit.

Assessments for subjects who have completed durvalumab and tremelimumab treatment and achieved disease control, or have discontinued durvalumab or tremelimumab due to toxicity in the absence of confirmed progressive disease are provided in APPENDIX 2.

Assessments for subjects who have discontinued durvalumab or tremelimumab treatment due to confirmed PD are presented in APPENDIX 3.

All subjects will be followed for survival until the end of the study regardless of further treatments, or until the sponsor ends the study.

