10.3.1 Study recording period and follow-up for adverse events and serious adverse events

Adverse events and serious adverse events will be recorded from time of administration of the first dose of investigational drug, throughout the treatment period and including the follow-up period (90 days after the last dose of durvalumab + tremelimumab).

During the course of the study all AEs and SAEs should be proactively followed up for each subject. Every effort should be made to obtain a resolution for all events, even if the events continue after discontinuation/study completion.

If a subject discontinues from treatment for reasons other than disease progression, and therefore continues to have tumor assessments, drug or procedure-related SAEs must be captured until the patient is considered to have confirmed PD and will have no further tumor assessments.

The investigator is responsible for following all SAEs until resolution, until the subject returns to baseline status, or until the condition has stabilized with the expectation that it will remain chronic, even if this extends beyond study participation.

Follow-up of unresolved adverse events

Any AEs that are unresolved at the subject's last visit in the study are followed up by the investigator for as long as medically indicated, but without further recording in the CRF. After 90 days, only subjects with ongoing investigational product-related SAEs will continue to be followed for safety.

AstraZeneca/MedImmune retains the right to request additional information for any subject with ongoing AE(s)/SAE(s) at the end of the study, if judged necessary.

Post study events

After the subject has been permanently withdrawn from the study, there is no obligation for the investigator to actively report information on new AE or SAEs occurring in former study subjects after the 90-day safety follow-up period for patients treated with durvalumab + tremelimumab. However, if an investigator learns of any SAEs, including death, at any time after the subject has been permanently withdrawn from study, and he/she considers there is a reasonable possibility that the event is related to study treatment, the investigator should notify the study sponsor and AstraZeneca/MedImmune Drug Safety.

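### Appendix 2 schedules no AE/SAE assessment after Month 3 for patients who stop for toxicity, although Section 10.3.1 requires their related SAEs to be captured until confirmed progression

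*Combined protocol and SAP*

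**What the plan says.** Section 10.3.1 sets an extended duty for one group: "If a subject discontinues from treatment for reasons other than disease progression, and therefore continues to have tumor assessments". For them, "drug or procedure-related SAEs must be captured until the patient is considered to have confirmed PD and will have no further tumor assessments".

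Appendix 2 is the follow-up schedule for two groups: patients who completed treatment with disease control, and "subjects who have discontinued durvalumab or tremelimumab due to toxicity in the absence of confirmed progression of disease". Its columns are headed "Time Since Last Dose of MEDI4736" and run Day 30, Months 2, 3, 4, 6, 8 and 10, then 12 months and later. The row "AE/SAE assessment" is marked at Day 30, Month 2 and Month 3 and is blank from then on. In the same table, subsequent therapy is checked to Month 10 and survival status is followed beyond that. Patients who stopped for toxicity are scanned "every 8-12 weeks until confirmed PD by RECIST 1.1 by investigational site review".

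Other text keeps to about 90 days:
- Section 10.3.1 puts the general AE/SAE recording period at 90 days after the last dose. It adds that, beyond this, safety follow-up continues only for patients with related SAEs that are still ongoing.
- Section 10.3.2 closes SAE reporting at 90 days or at the start of another anticancer therapy.
- Section 10.3.2.1 treats deaths after 90 days as survival events and not as SAEs.

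**The concern.** Safety and tolerability is the primary endpoint (Section 11.2.1), analysed in all enrolled patients with no stated time limit. Patients who stop treatment without progression can remain under observation for a long time, so they are the ones in whom a late immune-related or radiation-related SAE could still be seen. Section 10.3.1 appears to have been written for this group, but the schedule that a site works from does not carry the requirement. If sites follow the schedule, new related SAEs after Month 3 reach the database only when they surface by some other route. Missed events can only lower the reported toxicity. Section 11.3 relies on the upper confidence bound of the toxicity rate to exclude a clinically significant increase, so under-recording works in the favourable direction.

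**Working it through.** No statistical figure in the plan is at issue, so the check is mainly a comparison of text and schedule.

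**1. Does Appendix 2 govern these patients?** Yes. Section 8.1.3 says that assessments for those who completed treatment with disease control "or have discontinued durvalumab or tremelimumab due to toxicity in the absence of confirmed progressive disease are provided in APPENDIX 2". Section 4.3 says: "Subjects who are permanently discontinued from receiving investigational product will be allowed for safety per Appendix 2 or 3" (the sense is evidently that they are followed for safety).

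**2. Marks in the AE/SAE row of Appendix 2.** There are 8 columns. Marked: Day 30, Month 2, Month 3 = 3. Blank: Months 4, 6, 8, 10 and 12+ = 5. Month 3 matches the 90-day window and does not match the until-progression rule.

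**3. Scans without a scheduled safety question.** Month 3 to Month 12 is 9 × 52/12 = 39 weeks. At 12-week spacing, 39/12 = 3.25; at 8-week spacing, 39/8 = 4.9. That is about 3 to 5 scans for a patient who stays progression-free through Month 12.

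**4. Does anything else fill the gap?** The main schedule of assessments calls for AE assessment at every visit and has a long-term follow-up column, but Section 8.1 describes that schedule as covering screening and treatment. The post-study paragraph of Section 10.3.1 applies to patients permanently withdrawn from the study and asks only for notification of events the investigator happens to learn of. Neither schedules an assessment.

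**5. The passages side by side.**

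| Place | Capture period implied |
|---|---|
| 10.3.1, patients stopping for reasons other than progression | Related SAEs until confirmed progression |
| 10.3.1, general period and unresolved events | 90 days; afterwards only ongoing related SAEs |
| 10.3.2 | 90 days, or new anticancer therapy |
| 10.3.2.1 | Deaths after 90 days not reported as SAEs |
| Appendix 2, AE/SAE row | Month 3 |
| 9.1, sending patients withdrawn for reasons other than progression to Appendix 3 for tumour assessments | AE/SAE row of Appendix 3 also ends at Month 3 |

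One sentence stands against five other places, and the conflict begins inside Section 10.3.1.

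**6. Can the size be calculated?** Not from the documents. An illustration shows why.
- Number of patients: Section 1.4.2.3 reports 27 of 102 (26.5%) stopping for AEs on the combination, and 20 × 27/102 = 5.3. That figure pools cohorts given tremelimumab at 3 and 10 mg/kg. Section 1.3.1 says the 20 mg/kg + 1 mg/kg cohort, to which this trial's fixed doses correspond, had the fewest AE discontinuations.
- Risk of a related SAE between Month 3 and progression: no figure is given. Assume 5% to 10% per patient.
- Chance of at least one such event, 1 − (1 − p)^n: with n = 2, p = 0.05, it is 1 − 0.95² = 0.10. With n = 5, p = 0.05, it is 1 − 0.95⁵ = 0.23. With n = 8 (5 plus an assumed 3 completers), p = 0.10, it is 1 − 0.90⁸ = 0.57.

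A range of 10% to 57%, driven by assumed inputs, is not an estimate of bias. It also assumes that every patient is still progression-free after Month 3.

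**The case against.** Four objections deserve weight.

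**A blank cell does not forbid capture.** Section 10.3.1 still says related SAEs must be captured and asks for proactive follow-up of events, Section 8.1 allows more frequent evaluation, and scans go on. A reader might infer that late toxicity in these patients is simply not looked for, or that any site using Appendix 2 necessarily breaches Section 10.3.1. The documents do not support that. They support only the statement that no AE/SAE assessment is scheduled after Month 3.

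**Appendix 2 is not the sole outlier.** It agrees with most of the surrounding safety text. This stands, and it means that editing Appendix 2 alone would leave contrary sentences in force.

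**The effect on the headline rate is limited.** A reader might infer that one missed patient lowers the reported toxicity rate by 1/20 = 5 points. That holds only if the patient has no event already counted in that rate. Patients who stopped for toxicity mostly do, so a late SAE in them would mainly change a per-type percentage or a grade or seriousness category not yet reached. New anticancer therapy also moves patients to survival follow-up (Section 6.1.1), which shrinks the group further.

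**No decision rule depends on it.** DLTs are assessed early in treatment (Section 6.4 and synopsis), and the stopping rule ends 30 days after the last infusion (Section 3.3). This stands in full.

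None of these removes the contradiction between the two capture periods.

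**Conclusion.** The inconsistency is real and should be corrected. For patients who stop for toxicity without confirmed progression, Section 10.3.1 and Appendix 2 cannot both describe the intended safety follow-up. It would go too far to say the same of everyone on Appendix 2: the schedule also covers patients who completed treatment with disease control, and it is unclear whether the Section 10.3.1 wording about discontinuing includes them. The extended duty is also limited to drug- or procedure-related SAEs, so non-serious or unrelated late events are outside this point.

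The consequence is possible under-recording of late related SAEs for the primary endpoint. Its direction is known (downward) and its size is not. It bears mainly on toxicity rates by type, grade or seriousness. The conclusion rests on the text and the pattern of marks, not on the illustrative probabilities.

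**What to change.** 1. In Appendix 2, add a row for drug- or procedure-related SAEs, marked at every scan and contact already scheduled after Month 3 until confirmed progression, as Section 10.3.1 requires. Tie it to the scans as well as the contacts: the survival row is a phone contact for patients who decline to return, and the subsequent-therapy row has no mark in the column for 12 months and later.
2. Reconcile Section 10.3.1 (the until-progression sentence and the 90-day sentences), Section 10.3.2, Section 10.3.2.1, Section 9.1 and Appendices 2 and 3 to one stated capture period. Say whether completers with disease control are included, how a related death after 90 days is recorded, and which appendix applies to patients withdrawn for reasons other than progression.
3. State in Section 11.2.1 that related SAEs captured in this period enter the safety tables.

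The cost is one table row, one question at contacts that already take place, and wording changes in the sections listed. No new visits are needed.
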